6.4.5 Handling of Missing Data

Under the ITT framework, all research families' available data will be analyzed, even if incomplete. Full information maximum likelihood estimation, which fully utilizes all available data even if incomplete, will be used in analyses wherever possible. This approach yields correct statistical conclusions in the presence of missing data, as long as the data can be considered "missing at random (MAR)" (Little & Rubin, 2019). The MAR assumption implies that missing data elements can be treated as randomly missing as long a covariates relevant to the reasons (technically probability of being missing) are included in the models. Alternatively, if sample sizes are insufficient to support full information maximum likelihood estimation, then multiple imputation (MI), which is asymptotically equivalent, may be employed (Little & Rubin, 2019; Shafer, 1997).

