6.4.2 Sample Size Considerations

Assuming recruitment of 44 infant-parent dyads and allowing for a 9% (n=4) dropout rate, which is consistent with high retention rates (> 95%) in our prior intervention studies, 40 dyads (20 per treatment arm) will have complete data for analyses. Assuming a conventional type I error rate of .05, and intercorrelations among the repeated measures from .3 to .7, the magnitude of treatment group effects detectable with a .80 statistical power will range from $f=.37$ to $.42$, respectively, which are large standardized effects. The magnitude of time effects and time-by-treatment arm interaction effects detectable with a .80 power will range from $.27$ to $.18$, also respectively, which are medium-sized standardized effects. Thus, the study is underpowered to detect any but large differences

between the treatment arms and medium-sized or larger effects on time and time-by-treatment arm interactions. More important than the statistical comparisons, though, the analyses will yield key descriptive characterizations of the treatment-arm effects at the two posttest points (i.e., means, medians, proportions, and variances) on key outcomes, as well as effect size estimates that can be used in planning a larger scaled efficacy trial of the PIE intervention.

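### Full maximum likelihood is planned for about 40 dyads with no small-sample correction, so the stated .05 is not secured and large-sample tests would run at about .06 to .08

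*Combined protocol and SAP*

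**What the plan says.** Section 6.4.5 chooses the estimator: "Full information maximum likelihood estimation, which fully utilizes all available data even if incomplete, will be used in analyses wherever possible". It adds that this leads to correct conclusions provided data are missing at random. For samples too small for that estimator it offers a substitute: "if sample sizes are insufficient to support full information maximum likelihood estimation, then multiple imputation (MI), which is asymptotically equivalent, may be employed". No number of imputations and no degrees-of-freedom rule is given.

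Section 6.4.2 sets the error rate and the sample: "Assuming a conventional type I error rate of .05, and intercorrelations among the repeated measures from .3 to .7", with the expectation that "40 dyads (20 per treatment arm) will have complete data for analyses".

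Sections 6.4.1, 6.4.3 and 6.4.3.1 describe repeated-measures mixed models with terms for time, arm and arm-by-time. None of these sections names REML, Kenward-Roger or Satterthwaite degrees of freedom, or says whether tests refer to t/F or to z/chi-square. Section 6.4.3 does plan exact resampling tests, but the trigger is suspected non-normality or heteroscedasticity, not small sample size.

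**The concern.** Unrestricted maximum likelihood divides residual sums of squares by the number of dyads and makes no allowance for the estimated means, so variances come out too small. The usual Wald tests then compare the estimate with a normal or chi-square distribution, as if the variance were known. Both errors shrink standard errors or critical values, and at 20 per arm neither is negligible. Validity under missing at random is a separate, large-sample property and does not calibrate a test at this size.

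The plan declines any adjustment for multiple testing (6.4.3), so the level of each single test is the only error control left. The stated fallback does not close the gap by its own reasoning: a method justified because it agrees with maximum likelihood in large samples has not thereby been justified for small ones.

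**Working it through.** **Inputs.** From 6.4.2: alpha .05; 44 dyads recruited, 4 lost, 40 complete at 20 per arm; correlations .3 to .7; power .80. From 6.4.3.1: three occasions, with contrasts of Baseline to each posttest. Assumed here: normal outcomes, equal variances, compound-symmetric truth and, where there is dropout, dropout that depends on baseline and is split evenly between the posttests.

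**The plan's own figures.** A repeated-measures F test with N = 40 and m occasions has noncentrality f²Nm/(1+(m−1)r) between arms (1 and 38 df) and f²Nm/(1−r) for time and interaction (m−1 and 38(m−1) df). Solving for f at power .80 with m = 2:

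| r | between arms | time, interaction |
|---|---|---|
| .3 | .366 | .269 |
| .7 | .419 | .176 |

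These match the stated .37/.42 and .27/.18. With a chi-square reference the same formulas give .357/.408 and .262/.172, which round to .36/.41 and .26/.17 and miss all four stated values. The power section therefore appears to rest on finite-df F tests. (The match is for two occasions; three give .332/.407 and .242/.158, which is a separate matter.)

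**Closed form, complete data, maximum likelihood with large-sample tests.**

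- *Single change contrast, unstructured covariance.* The maximum likelihood variance uses divisor n instead of n−2, so |z| > 1.96 is the same event as |t| > 1.96·√((n−2)/n) on n−2 df. For n = 40: 1.96·√(38/40) = 1.910, and P(|t₃₈| > 1.910) = .064. For n = 44: .062.
- *Single contrast, compound symmetry, three occasions.* P(|t₇₆| > 1.96·√(76/80)) = .060.
- *2-df arm-by-time test, unstructured.* By Hotelling's T², the cut-off 5.99 becomes F = 5.99·(38/40)·37/76 = 2.77 on 2 and 37 df, and P = .076.
- *Interval width.* 1.910/2.024 = .944 at n = 40, and .949 at n = 44. Intervals are 5% to 6% too narrow, with coverage of 93.6% to 93.8%.

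**Simulation under the null.** Three occasions, unstructured covariance, saturated means. Settings: 44 dyads with 4 dropouts at r = .3 and r = .7 (6,000 runs each), and 40 complete dyads at r = .5 (10,000 runs). The Monte Carlo standard error is about .003 and .002. Imputation (20 imputations) was run only in the settings with dropout.

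| Method | single contrast | 2-df test |
|---|---|---|
| ML, z or chi-square | .061–.070 | .072–.078 |
| ML, t | .053–.062 | – |
| REML, z or chi-square | .055–.063 | .063–.070 |
| REML, t | .047–.056 | – |
| Imputation, classical Rubin df | .053–.059 | – |
| Imputation, Barnard-Rubin df | .045–.051 | – |

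The mean width ratio of the ML z interval to the REML t interval was .944. Either repair alone (REML, or a t reference) removes part of the excess; both together bring the level close to .05.

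**The case against.** The plan never says that it will use z or chi-square tests, and its power figures reproduce with finite-df F tests. The phrase about full information sits in the missing-data section, where the natural contrast is with discarding incomplete records, not with REML. On that view the plan is under-specified but not wrong. This stands in part. A reader might infer that the plan as written produces inflated error. The documents do not support that, because the reference distribution is left open and a t reference removes much of the excess. But the literal estimator is maximum likelihood, and even with t it gives .056 in closed form at n = 40.

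A reader might also infer that the imputation fallback yields narrow intervals and should go. The numbers point the other way: imputation was better calibrated than maximum likelihood with z. Only its rationale and its missing details are at fault.

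A third tempting inference is that the effect sizes meant for planning the next trial would be seriously distorted. With complete data the contrast estimates are the same under both estimators, and the standard deviation is low by a factor √(38/40) = .975. A standardized effect of .40 would read about .41. The documents speak of descriptive summaries and effect sizes for planning, not of confidence intervals.

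Finally, the study is proof-of-concept, ranks description above testing (6.4.2) and puts missed signals ahead of false ones (6.4.3). That lowers the stakes. It does not settle the matter, because that passage concerns adjustment across tests, not whether a single test holds its nominal level. The resampling route may apply to some of the proportions, counts and ratings, but small numbers alone do not trigger it.

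**Conclusion.** The point holds conditionally and is modest in size. With unrestricted maximum likelihood and large-sample tests at about 40 dyads, type I error is about .06 to .07 for single contrasts and .07 to .08 for 2-df tests, and 95% intervals are about 5% to 6% too narrow. With a t reference, error is about .053 to .062. These figures rest on normal outcomes with equal variances and on the dropout pattern assumed above. The plan's reason for choosing imputation in small samples is not valid, though imputation itself performs acceptably. This is a cheap improvement, not a flaw that threatens the study's conclusions.

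**What to change.** In 6.4.3 and 6.4.5, state that the Gaussian mixed models are fitted by REML, with t and F tests on Kenward-Roger (or Satterthwaite) degrees of freedom. This uses every available record under the same missing-at-random assumption. It does not carry over to the Poisson or negative binomial fallback in 6.4.3.2, which needs its own statement of method.

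In 6.4.5, remove asymptotic equivalence as the ground for using imputation in small samples. If imputation is kept, state the number of imputations and use Barnard-Rubin degrees of freedom.

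The cost is a few sentences and a software option. Intervals become slightly wider, and no further data are needed.

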7.1 Ethical Considerations: Informed Consent/Accent and HIPAA Authorization

Incentives

- Families participating in the study will receive a small monetary incentive to participate. We have budgeted for a 20 dollar gift certificate for the first assessment (Baseline), 25 dollars for the second assessment (Posttest-1), and 50 dollars for the third (Posttest-2). We will also provide families with a 10 dollar gas card at each assessment visit.
- Families will receive the specified incentive at each assessment visit. If a family withdraws from the study they will not receive the subsequent incentive(s).
- Both children and their parents will participate in our study. The incentive payments will be made to the parents.
- Potential for coercion: The incentives are intended to cover the parents/guardians' time for study participation, incidental expenses and for travel (gas card) for each visit. The incentives increase slightly to increase retention of the sample to the conclusion of the study. The participants will receive 95 dollars in incentives for approximately four hours of assessment. According to data released in 2016 by the NC Department of Commerce, the average hourly wage in NC is 21.24. Thus the incentive offered for assessment visits, considering travel time, is in-line with what an average wage-earner would get for this amount of time. No incentives are planned for the in-home intervention sessions.
- Privacy considerations: We will not collect Social Security Number information for the purposes of offering these incentives.
- Costs to be borne by the participants: The only potential costs to participants related to study participation will be any missed employment compensation due to their participation in home intervention sessions and assessment visits. Additionally, the gas cards may not fully compensate

all participants for their travel to the assessment site, depending on the distance they will travel and the fuel efficiency of their vehicle.

- Alleviating potential costs to participants: A postage paid envelope will be provided with any hard copies of the FYI or other assessment materials for families to return the documents at no cost to them; a similar envelope will be provided to families to return consent for intervention forms if these are not signed at the study offices.

Informed Consent:

- The informed consent process is described in detail in section 6.3.2 of this protocol.
- Completion of the FYIv3.1b is considered to entail implied consent for use of the data. Both the mail and online version of the FYI will include a cover page that is a fact sheet about the FYI and larger study. All information typically included in an informed consent form is described in the page, including confidentiality, risks, and benefits of the study. It is our understanding that a parent who reads the page and submits the questionnaires give us their consent to use their data. Only families who answer "yes" to the question "would you be willing to be contacted about future research" will be contacted in the event their child scores at-risk on the FYI.
- Written informed consent will be obtained for the baseline assessment and for the intervention (consent to be obtained separately for baseline assessment and intervention, because some infants will not meet criteria at the baseline assessment for inclusion in the intervention trial).
- Consent documents are attached, including (a) the cover letter for the FYIv3.1b; (b) the consent form for the baseline assessment, and (c) the consent form for intervention.
- The child participants will not provide written assent due to their young age (11-16 months old at study entry) and related inability to understand the study purpose or procedures.

Collection of identifiers and sensitive information; confidentiality

- We will collect names, mailing/street addresses, telephone numbers, and email addresses for the purposes of contacting families about the study.
- We will collect full face video images of parents and children for the purpose of measuring study outcomes.
- Identifiers coded with a linkage file will be stored electronically in a different folder from the research data collected on participants. Access to the folder with the linkage file will be restricted (via electronic permission settings) to the MPIs and the Study Coordinator. The Study Coordinator will provide the necessary contact information to the interventionists for the respective families assigned to each interventionist.
- Screening measures and protocols from the developmental assessments will be stored in a locked file cabinet in a locked office and identified only by dyad ID number. Any scientific reports, article submissions, or summaries of the data will not include names. Additionally, individual data that might possibly identify any one child or parent will not be presented; data will be presented in summary format that will preclude any personal identification. In some cases, parents may give permission to use short segments of video for teaching/educational purposes. All videos will be kept secured in the PI's laboratory, identified by ID number, and archived. Video files will be clearly marked to identify whether the parent has given permission to use them for teaching/educational purposes. We will not share identifiable data with any other party (such as a care provider or physician) without written consent from the parent/guardian. However if a parent/guardian chooses to share the written report that we provide to them, they will

be made aware that this information may then become part of their child's record with that institution, which may provide Insurance companies with access to that information.

- Electronic data will be stored on a secure and encrypted network (REDCap) that requires password access.
- Portable computing devices will be encrypted, have a power-on password required, and an automatic log-off.
- The primary potential for deductive disclosure will come from our videotaping of research participants, which is essential for several aspects of the study protocol. Because the videotapes will have full face images of children and their parents, and because first names will be used often in the course of interactions captured on videotapes, the identity of participants could be deduced by someone watching the videotapes. We, therefore, will take careful measures to protect the security of the videotapes.
- Study personnel will have access to physical data (paper forms, DVD, external hard drives) that will be housed in the PIE office in locked cabinets. Staff will be required to sign out/in any form of these data (information recorded in dyad's individual paper file or on DVD) in a notebook. All electronic data will be available on a secure network drive that is password protected and encrypted (REDCap, School of Medicine shared drive, UNC Office 365 suite of secure cloud applications). The deidentified data will be available through the secured network and the identifying match will be housed separately. Access to the data files will be restricted, based on the role of the research team member. For example, members of the assessment team will not have access to data related to the intervention, in order to preserve their "blindness" to the randomized group assignment of study participants.

Privacy

- Phone interviews in the PIE office will be conducted behind closed doors.
- Assessments will be conducted in a private suite.
- No mailed information will include any indication of child/parent status that is visible on the exterior of the envelope.
- Coaching sessions will take place in the family's home, scheduled at the convenience of the parent.

7.2 Institutional Review Board (IRB) Review

The study will undergo review and approval by the UNC-CH IRB, with the application submitted through the online application system (IRBIS).

Modifications will be submitted for UNC-CH IRB review through the online system, and IRB approval will be secured before modifications are implemented.

Reportable events and unanticipated problems under the purview of the IRB will be reported following UNC-CH Standard Operating Procedures.

7.3 Subject Privacy, Confidentiality & Data Management

See section 7.1 for the protocol related to participant privacy and confidentiality and data security.

Data will be entered and stored in RedCap. Parent report measures will be entered directly into RedCap by participants, unless the participants request to complete hard copies of these measures instead.

Other data will be entered into RedCap by trained research assistants who will be granted limited access to the RedCap site consistent with their data entry role. One research assistant will enter the data initially, and a second research assistant will independently check the data entry for errors.

Access to names, home addresses, email addresses, and phone numbers entered into RedCap will be restricted to the data manager, project PIs, and study coordinator; the project PIs or study coordinator may provide temporary access to this information for other study staff if needed to complete an assigned task.

Data entry records will be identified by each participating dyad's unique ID number.

7.4 Deviations/Unanticipated Problems

A log of protocol deviations will be maintained through active data collection. Any protocol deviation that harms a participant or places others at increased risk of harm will be reported to the IRB per UNC-CH SOP 1401.

Reportable deviations or unanticipated problems will be reported to the IRB through the online reporting system within two weeks of the PIs becoming aware of the problem.

Any protocol deviation that is made to eliminate an immediate hazard to a participant without IRB approval will be subsequently reported to the IRB per UNC-CH SOP 1401.

Any unanticipated event that involves risk to a participant or others will be reported to the IRB per UNC-CH SOP 1401. For this purpose, unanticipated events are defined as follows (from UNC-CH SOP 1401):

1. Unanticipated Problem Involving Risk to Subjects or Others (UPIRSO): Any incident, experience, or outcome that
 1. 4.5.1 is unexpected (in terms of nature, severity, or frequency) given (a) the research procedures that are described in the protocol-related documents, such as the IRB-approved research protocol and informed consent document; and (b) the characteristics of the participant population being studied;

2. 4.5.2 is related or possibly related to a participant's participation in the research; and
3. 4.5.3 is serious or suggests that the research places participants or others at a greater risk of harm (including physical, psychological, economic, or social harm) than was previously known or recognized.

7.5 Data Collection

Data collection information has been previously detailed in sections 5.2, 6.1.3, 6.3.5, and in the Visit Schedule Table.

Data will be securely archived in RedCap.

The linkage file will be maintained until videos of the dyads have been destroyed. Access will be restricted to the study PIs or other research staff they designate, based on need to access the linkage files.

Videos of dyads will be destroyed before the child reaches the age of 18.

7.6 Data Quality Assurance

All research staff will complete training in human subjects research ethics.

Each research staff member will be trained to complete activities related to their role(s) on the project by a qualified trainer, with ongoing oversight. In addition to key personnel (MPIs and Co-Is, including study methodologists/statisticians), project roles will include a study coordinator (with overall responsibility for recruitment, enrollment, informed consent, scheduling visits, data storage, data entry, and training and supervision of RAs involved in these activities), lead coach (responsible for training and oversight of project coaches), an assessment coordinator and assessment team leads (responsible for organizing and providing assessor training and leading individual assessment visits), and coding team leaders (responsible for training RAs and monitoring and maintaining their reliability for measures involving coding/rating/scoring of videos).

The lead coach, assessment coordinator, and coding team leaders will each ensure that team members fulfilling roles under their purview have completed all required training steps and met criteria for fidelity in administering assessments, implementing intervention, and/or reliability in scoring/rating/coding as required for the purpose of data quality.

To simplify the process of reliable coding/rating of measures taken from videos, all activities related to one measure will be focused either at UNC-CH or at USC, to minimize the need for cross-site training on coding or rating the same measure.

For measures that are not entered directly into RedCap by parents, data will be entered by

one research assistant and independently check for accuracy by another research assistant. Verification that data entered for a participant's measure have been checked will be recorded within RedCap.

Prior to analysis, data will be cleaned and any inconsistencies will be addressed.

7.7 Study Records

Study records include:

Completed FYI3.1b

Short Demographic Questionnaire (completed in conjunction with the FYI3.1b)

Contact information for parents who complete the FYI3.1b

Long Demographic Questionnaire (completed by participants who consent to baseline assessments)

MacArthur Communication Development Inventory (baseline)

Parent Stress Scale (baseline)

Sensory Experiences Questionnaire (baseline, Posttest-1, Posttest-2)

Mullen Scales of Early Learning

- Visual Reception Scale (Baseline)
- Fine Motor Scale (Baseline)
- Receptive Language Scale (Baseline, Posttest-1, Posttest-2)
- Expressive Language Scale (Baseline, Posttest-1, Posttest-2)

Parent-Child Interaction Session (Baseline, Posttest-1, Posttest-2)

- Videos of session
- Dyadic Engagement (coded from videos, using Observer software)
- Parent Responsivity to Child Sensory Reactivity Cues (rated from videos)
- Parent Responsivity to Child Prelinguistic Communication Cues (rated from videos)
- Child Intentional Communication (coded from videos, using Observer software)

Child-Directed Speech Protocol (Baseline, Posttest-2)

- Videos of session
- Gazepoint records (eye-tracking during child-directed speech protocol)
- Firstbeat records (interbeat-interval)
- Shimmer records (skin conductance levels)

Brief Observation of Social Communication Change (Baseline, Posttest-2)

- Videos of session
- Scoring protocols completed from videos

Sensory Processing Assessment (Baseline, Posttest-2)

- Videos of session
- Scoring protocols

Response to Joint Attention Scoring protocols (Baseline, Posttest-2)

Developmental reports for children (Baseline, Posttest-2)

PIE Coaching fidelity videos

PIE Coaching fidelity scoring protocols

Videos of parent-infant routines used for coaching

PIE Coach session plans

PIE Family action plans

Interview notes from final coaching session exit interview

PIE intervention rating profile

